Scientific Rigor: The team will adhere to qualitative research processes to ensure the credibility, confirmability, dependability, and transferability of the qualitative data from these analyses. To support the credibility of the data, we will conduct peer debriefing. We will also use "member checks," i.e., sharing of initial data

interpretations with participants to ensure accurate interpretations. Triangulation of findings, along with reflexivity, will enhance the confirmability of the interpretations. The investigators will carefully record an audit trail and keep extensive field notes to facilitate transferability of study findings into other contexts.

RISKS, BENEFITS & MONITORING

Risks to Human Subjects

Research Environment and Commitment to Protection of Human Subjects:

Columbia University Irving Medical Center (CUIMC), Birmingham AIDS Outreach (BAO), and University of Alabama at Birmingham (UAB) are committed to safeguarding the rights and welfare of human subjects in all research activities, and all have a current Assurance of Compliance with the Office for Human Research Protections (OHRP). The investigators will follow all required policies related to the protection of human subjects. All investigators have fulfilled human subjects protection and Health Insurance Portability and Accountability Act (HIPAA) training requirements (including CITI basic and refresher courses, Good Clinical Practices, and conflicts of interest) and are up-to-date with these certifications. The study described in this application will be reviewed and approved by Western Institutional Review Board (IRB), and we will seek reliant review at UAB and BAO (to fulfill the single IRB policy) prior to any participant recruitment or data collection activities. All prospective participants will be fully informed of the intent of the study and expectations of participants prior to enrollment using an IRB-approved informed consent form.

Human Subjects Involvement, Characteristics, and Design

Characteristics of the Population:

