A detailed monitoring plan will be included as part of the study protocol, submitted to the IRB, and reviewed and approved by the funding Institute and Center before the study begins. Prior to initiation of the study, agreement about the data safety monitoring plan will be confirmed to ensure the safety of subjects and the validity and integrity of the data. The research coordinator at each site will report serious adverse events (SAEs) that are unexpected and study-related immediately to a study physician who will convey this information to the study team, IRB, and NIH. All AEs and SAEs will be captured, reports will be completed, and information will be entered into the study database. A safety report will detail all serious and unexpected AEs or other unanticipated problems that involve risk to study participants or others and whether these appeared to be related to the study-based interventions or research assessment protocols. If the study team, CUIMC or UAB IRB, or NIH has concerns regarding SAEs, the Western IRB will be notified and a copy of the safety summary will be filed with both IRBs. Actions taken by the Western, CUIMC, or UAB IRB offices in response to AE concerns will be reported to the NIH. All AEs will be reviewed every six months, or sooner, with the designated safety officer.

Vulnerable Subjects:

Economically and/or educationally disadvantaged persons will be enrolled. While this group is considered a vulnerable population, the study team has considerable experience enrolling these participants. As these groups carry the burden of the majority of HIV incidence in both study sites and demonstrate considerable challenges with achieving optimal HIV health outcomes, it is important that they are not excluded from participation in this study. Additionally, our study will analyze the potential impact of the intervention(s) on racial and ethnic groups, perhaps providing new information on the disproportionate impact of HIV felt by these populations.

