The study will be conducted according to Good Clinical Practice (GCP) guidelines, the U.S. Code of Federal Regulations (CFR) Title 21 CFR (Part 50 – Protection of Human Subjects and Part 56 – Institutional Review Boards) and the Declaration of Helsinki. This protocol will be submitted to the IRB at the Western IRB for approval and will be reliably reviewed at UAB. The informed consent of each subject will be obtained in accordance with 21 CFR Part 50 and the Declaration of Helsinki before protocol-specified procedures are carried out.

A study research assistant will obtain the participant's written informed consent prior to any study-related procedures. Consent will be documented by the dated signature of the subject. The signature confirms that the consent is based on information that has been understood. Each subject's signed informed consent form will be kept in secure files by the investigators for possible inspection by regulatory authorities.

Potential Benefits of Proposed Research to the Participant and Others

The potential benefits to an individual participant in the study are not known. The potential benefits of the study to others could be considerable. If our hypotheses are true, this study will make a significant contribution towards helping PLWH who are virally unsuppressed improve adherence to their antiretroviral therapy (ART) regimen and ultimately achieve viral suppression. If the intervention is effective, the direct benefit to participants is the increased ART adherence, retention in HIV primary care, and viral suppression. Increasing ART adherence for PLWH will yield significant benefits in current efforts to achieve HIV elimination. Possible risks (i.e., discomfort answering questions, potential confidentiality breaches) are outweighed by the new knowledge gained regarding increasing ART adherence among PLWH.

Importance of Knowledge to be Gained

The knowledge gained from this research will enable the scientific community, clinicians, and PLWH to improve the HIV care continuum in the US. Consistent with the priorities of RFA-NR-20-002, findings from this study will focus on the efficacy of an adaptive Community Health Worker intervention to improve HIV care among PLWH.

Data and Safety Monitoring Plan

Data and Safety Monitoring Plan is attached separately.

ClinicalTrials.gov Requirements

This trial will be registered with ClinicalTrials.gov.

References

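### Only SAEs already classed as unexpected and study-related go at once to a physician; the text names no assessor, and other SAEs have no review timing except the safety officer's, every six months or sooner

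*Combined protocol and SAP*

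**What the plan says.** The rule is in the protocol section Unexpected and Serious Adverse Event Reporting. Its immediate route reads: "The research coordinator at each site will report serious adverse events (SAEs) that are unexpected and study-related immediately to a study physician". The physician then informs the study team, the IRB and NIH. The same section has four further provisions:

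- **Capture.** "All AEs and SAEs will be captured, reports will be completed, and information will be entered into the study database".
- **Safety report.** It covers serious and unexpected AEs and other unanticipated problems, and states "whether these appeared to be related to the study-based interventions or research assessment protocols".
- **Escalation.** "If the study team, CUIMC or UAB IRB, or NIH has concerns regarding SAEs, the Western IRB will be notified".
- **Periodic review.** "All AEs will be reviewed every six months, or sooner, with the designated safety officer".

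The section opens by promising a detailed monitoring plan, to be approved by the funder before the study starts. Near the end of the protocol, the section on that plan says only: "Data and Safety Monitoring Plan is attached separately". The plan is not among the documents available for this review.

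On ethics review, the section Research Environment and Commitment to Protection of Human Subjects says that the study "will be reviewed and approved by Western Institutional Review Board (IRB), and we will seek reliant review at UAB and BAO". The closing paragraphs under Vulnerable Subjects also send the protocol to Western, and there name UAB alone as the relying site.

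**The concern.** Expectedness and relatedness are normally results of a medical assessment. Here they are conditions for the event to reach the physician at all. If an event is misclassed at that point, no later step with a date attached would bring it to medical attention before the periodic review.

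Such events are foreseeable in this population. The trial measures depression, anxiety and substance use as moderators. The Potential Risks section makes counselling available if a participant enters crisis, and lists syncope as a rare effect of a blood draw. By way of illustration, a psychiatric admission or overdose taken to be unrelated, or a serious syncope taken to be expected, would fall outside the immediate route.

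The protocol's other stated check on harm does not cover this. The Efficacy rows of Table 5 look for unintended consequences in withdrawal notes and complaints notified to the IRB, not in SAE data.

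**Working it through.** No power, alpha or margin figure is involved. The check sets the provisions of the reporting section side by side.

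**Step 1. Route for each class of SAE.**

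| Class of SAE | Immediate report to physician | Named in safety report | Open to escalation | Only stated review timing |
|---|---|---|---|---|
| Unexpected and related | Yes | Yes | Yes | Immediate |
| Unexpected, not related | No | Yes, undated | Yes, undated | Six months or sooner |
| Expected, related | No | Not as an unexpected AE | Yes, undated | Six months or sooner |
| Expected, not related | No | Not as an unexpected AE | Yes, undated | Six months or sooner |

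All four classes are captured in the database. The table assumes that the periodic review of all AEs includes SAEs.

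**Step 2. Who classes the event.** The immediate-route sentence names a reporter (the coordinator) and a recipient (the physician). The two conditions apply before the report is made, so the sorting precedes the physician. No sentence names the person who sorts. The safety report addresses relatedness, again without an assessor or a date.

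**Step 3. Length of the permitted wait.** The outer limit for periodic review is six months. The longest wait is therefore about 6 months, for an event just after one review with no earlier review called. If events fell evenly between reviews exactly six months apart, the mean wait would be 6 / 2 = 3 months. The Design Overview gives the intervention as six months, so the longest wait equals one participant's whole intervention period. The text allows an earlier review but states no trigger for one.

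**Step 4. The IRB wording.** The reporting section names three boards (Western, CUIMC and UAB), yet says "the Western IRB will be notified and a copy of the safety summary will be filed with both IRBs". The immediate route refers to the IRB without naming it. BAO is a relying institution in the Research Environment section and, under Procedures, part of the Alabama visit site, but it does not appear in the reporting section.

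**The case against.** The strongest objection is the separate Data and Safety Monitoring Plan. The reporting section is a human-subjects summary, and assessor roles and SAE timelines may sit in that plan. This stands: the gap is shown for this document only. It does not make the sentence harmless, because a site could follow it as the working rule.

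A reader might infer that a non-physician makes the causality call. The documents do not support that. They say who reports, not who assesses, and they do not give the coordinator's qualifications. What remains is the order of steps and the unnamed assessor.

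The section also contains real safeguards. An unexpected death thought unrelated would still appear in the safety report with its relatedness addressed. The study team can escalate concerns about any SAE, and the periodic review can be brought forward. These soften the gap. They do not close it, since none has a deadline or names a medical assessor.

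A reader might also infer that Western hears of an event only if some other body first has concerns. That misreads the section. The immediate route already goes to the IRB, most naturally Western as the reviewing board. The concerns sentence adds a second route, and the study team itself can start it.

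Finally, no blinding is described and staff open the assignment envelopes, so one might expect relatedness calls to distort a comparison by arm. The plan has no by-arm list of related SAEs, and nothing says that the physician is blinded either. That argument adds nothing here.

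**Conclusion.** The point holds for the text available. The immediate route to a physician is limited to SAEs already classed as unexpected and study-related, the assessor is not named, and every other SAE has only the review due every six months or sooner. The size is a permitted wait of up to about six months, on the assumptions that no earlier review is called and that the separate plan sets nothing tighter.

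How many events would be affected cannot be derived, because the documents give no SAE rate. A reader might suppose that nearly all SAEs would miss the immediate route, but no figure supports that.

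The Potential Risks section describes the study activities as minimal risk, which limits the practical weight. It does not remove the reason for prompt medical judgement on whether a serious event is related. The efficacy analysis is unaffected. The wording should be changed because the change is small and bears on participant safety. The IRB wording is a minor clarification.

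**What to change.** Reword the immediate-route sentence along these lines: *The research coordinator at each site reports every SAE promptly to the study physician, whatever its suspected cause. The physician judges and records expectedness and relatedness, and conveys SAEs that are both unexpected and related to the study team, the IRB and NIH.* Check this against the Data and Safety Monitoring Plan so that the two agree on assessor and timing, and add a cross-reference.

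As a minor clarification in the same edit, state that the IRB in the immediate route is Western. Say which boards are meant where the section speaks of two, and reconcile the absence of BAO with the reliance arrangements stated elsewhere.

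The cost is a wording change and some extra reading for a physician already in the plan. For workload only, suppose that 5% to 15% of the 300 participants had at least one SAE over 12 months. That would be 300 × 0.05 = 15 to 300 × 0.15 = 45 participants. These rates are an assumption, not a figure from the documents, and the conclusion does not depend on them.
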